9 STATISTICAL CONSIDERATIONS

9.1 *Study Design and Aim*

This study is designed as a feasibility companion protocol that will use the data generated by BMS' studies of BMS-986036 under protocols MB130-068 and MB130-069 for which one of the exploratory objectives is to assess whether BMS-986036 compared to placebo improves liver metabolic function as assessed by the ¹³C-Methacetin Breath Test.

Additional analyses may be performed by Exalenz on the data to be received from these BMS studies. The study is feasibility for drug response monitoring however the data may be used for Exalenz for future submissions.

9.2 *Endpoint Measures*

9.2.1 *Primary endpoint measure*

In order to show the ability of the MBT to measure the effect of BMS-986036 treatment on the metabolic capacity of the liver after 24 weeks, 48-weeks, as compared to changes in placebo treated subjects the primary endpoint will be analyzed using a Mixed Effect Repeated Measures (MMRM) Model. An unstructured correlation matrix will be used to model within-patient errors and restricted maximum likelihood estimation will be used. The Kenwood-Roger method will be used for the denominator

| | |
|---|---|
| Exalenz Bioscience Ltd. | Last update: February 20, 2018 |
| Study Title: Companion protocol for the ¹³C-Methacetin Breath Test (MBT) for use in Bristol-Myers Squibb phase 2b studies for BMS-986036 (PEG-FGF21), under Protocols MB130-068 and MB130-069 | Protocol: BMS-EX-0118 Version: 1.0 |
| Document No: CSP000002 | Page 29 of 38 |

degrees of freedom. Should the model fail to converge with an unstructured covariance matrix, Toeplitz and Compound-Symmetric structures will be applied.

The MMRM model will include change from baseline as outcome, and Study Arm, Visit, Study Arm*Visit Interaction, Baseline value and site as covariates.

Assessments will be done for each study cohort independently and according to availability and on the combined population of the two study cohorts by dose of the BMS drug under study.

A sensitivity analysis of the primary endpoint will be performed excluding subjects with significant protocol violations. Additional sensitivity analyses will be performed if deemed necessary. Such analyses as well as additional details will be described in the SAP.

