9.3 Acceptance Criteria (Study Hypotheses)

At least one cut-off in changes of MBT values will be determined to show that MBT is a potential measure that can assess the response to treatment for BMS-986036.

At least one cut-off, to be determined by the algorithm being developed by Exalenz using data from IDE# G080227, will be validated in this study to classify Subjects into risk groups for deterioration of liver function related events.

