SAP for Protocol BMS-EX-0118: Companion protocol for the ¹³C-Methacetin Breath Test (MBT) for use in Bristol-Myers Squibb phase 2b studies for BMS-986036 (PEG-FGF21), under Protocols MB130-068 and MB130-069	Document Version: 1.0
Document Nº: CSD00114	Page 8 of 21

for the study will be descriptive by nature. No formal statistical testing will be performed. Nominal p-values from statistical tests will be reported for supplementary information.

When differences exist in methods, descriptions or explanations provided in the protocol and this SAP, the SAP prevails.

Since this study is a companion to a pharmaceutical company's study, the data management for the main study can independently determine as to when a data freeze or a data lock shall be performed. Therefore, for the Exalenz companion protocol purposes, any amendments to the SAP will be made prior to Exalenz independently accessing the data from the database freeze or lock, if available. In case additional analyses not described in the final SAP or deviations from the final SAP are required, they will be documented in the Clinical Study Report (CSR).

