However, as aforementioned in the Introduction (section 2), the enrollment phase and all MBT testing (incl. Day1, Week 24 and Week 48 visits) for the aforementioned BMS sponsored studies has been completed. The data is still being assessed by BMS and the respective databases are planned to be made available to Exalenz between July and November 2021, after their respective data lock and release from BMS.

The initially planned sample size of 250 subjects, per statistical section in the companion protocol, was not reached for multiple reasons:

- The MBT testing as part of the BMS studies, was an opt in substudy, requiring an additional consent process. Subjects enrolled to the BMS studies were reluctant to add an additional investigational test to their study schedule.
- The COVID-19 outbreak further complicated the enrollment and especially the follow up testing of already enrolled subjects, as visits were more and more conducted remotely and any breath testing was avoided during in person visits.

Since the actual final sample size of subjects with valid MBT results at baseline and post-treatment phase, across both BMS studies, is expected to be lower than 80, the statistical analyses for the study will be descriptive by nature. No formal statistical testing will be performed. Nominal p-values from statistical tests will be reported for supplementary information.

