5 GENERAL CONSIDERATIONS FOR HANDLING OF MISSING DATA

5.1 *Premature Withdrawal and Missing Data*

For patients who are withdrawn from the study prior to study completion, all data compiled up to the point of discontinuation will be used for analysis. All withdrawals will be included in all analyses up to the time of withdrawal.

There will be no imputation for missing data.

The study variables cannot be evaluated for subjects for whom BreathID® MCS device MBT results are not available and therefore these subjects will be left out of the efficacy analysis. Subjects missing clinical outcome or biopsy results or other endpoints will be excluded from the respective analyses.

Meridian Bioscience Israel Ltd.	Last update: May 05, 2021
SAP for Protocol BMS-EX-0118: Companion protocol for the ¹³C-Methacetin Breath Test (MBT) for use in Bristol-Myers Squibb phase 2b studies for BMS-986036 (PEG-FGF21), under Protocols MB130-068 and MB130-069	Document Version: 1.0
Document Nº: CSD00114	Page 14 of 21

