8 STATISTICAL ANALYSES

8.1 *General Considerations for Data Analyses*

All analyses will be performed using either SAS® v9.4 or higher (SAS Institute, Cary NC, US) or the R software version 4.0.3 or higher (R Development Core Team. Vienna, Austria).

The standard summary statistics for continuous variables are: N, mean, standard deviation, median, minimum and maximum. The standard summary statistics for categorical variables are: count and proportion.

The analyses will be descriptive by nature, nominal p-values will be reported for supplementary information. Any statistical tests performed, will be two-sided. The significance level of findings will be equal to or lower than 5%. Where confidence limits are appropriate, the confidence level will be 95%. Nominal p-values and unadjusted confidence intervals will be presented.

8.2 *Baseline Definitions*

The study baseline will be defined as the Day 1 visit value, unless specifically mentioned otherwise. In case of repeat measurements, the latest value associated with the Day 1 visit will be considered the baseline value.

For survival models: The baseline MBT test will be defined as the baseline and day 0 of follow up.

8.3 *Disposition of Patients*

Subject dispositions will be summarized based on all subjects screened into the study separated by study cohort (and combined), and for each treatment group.

The following subject disposition information will be presented:

- The number and percentage of subjects who had valid MBT for each visit.
- The number and percentage of reasons for not having a valid MBT for each visit.
- The number and percentages of subjects that were excluded from the EA and mEA analysis sets, by reason for exclusion.

Meridian Bioscience Israel Ltd.	Last update: May 05, 2021
SAP for Protocol BMS-EX-0118: Companion protocol for the ¹³C-Methacetin Breath Test (MBT) for use in Bristol-Myers Squibb phase 2b studies for BMS-986036 (PEG-FGF21), under Protocols MB130-068 and MB130-069	Document Version: 1.0
Document Nº: CSD00114	Page 16 of 21

8.4 *Efficacy Analyses*

8.4.1 *Primary Endpoint*

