In order to show the ability of the MBT to measure the effect of BMS-986036 treatment on the metabolic capacity of the liver after Week 24 and Week 48 visits, as compared to changes in placebo treated subjects, the primary endpoint will be analyzed using a responder analysis, where any increase of MBT value will be considered as a response while a same value or a decrease of the MBT value will be considered as non-response.

The primary analysis will be conducted on the mEA set, with the PDR_{peak} and cPDR₃₀ responder rate of Week 24 and Week 48 of data from both BMS' studies.

Individual analyses for each cohort separately will also be reported.

8.4.2 *Secondary Endpoints*

8.4.2.1 *Prognostic Value of MBT in Overall Event-Free Survival*

In order to assess the prognostic value of MBT in prediction of liver disease deterioration (reported as liver-related clinical outcome events), the endpoint measures will be point estimates of Cox Regression's Hazard Ratio for classifying Subjects into risk groups for clinical deterioration with respective exact two-sided 95% confidence intervals in the placebo and treatment arms as determined by MBT. The MBT parameter to be used to predict liver-related clinical outcome events is PDR_{peak}. Any PDR_{peak} value of less or equal to 20 %/h (see **Appendix A** for detailed description of parameter calculation) will be considered as 'high risk' and any value above that threshold will be considered as 'lesser risk' (additional cut-off values may be explored). The dichotomic MBT result will be tested for significance using the Cox proportional hazards regression model with site and randomized arm as covariates. If the randomized arm factor is found non-significant (i.e. p-value > 0.05), then this factor will not be a covariate for the main analysis to be performed. If the randomized arm factor is found statistically significant (i.e. p-value ≤ 0.05), then the main analysis will be performed keeping this factor as a covariate (to 'adjust' the analysis for treatment).

The time-to-first event will be derived as the number of days between the Day 1 MBT test and the date when the first event occurs or when a subject is censored (i.e., event/censored date minus

Meridian Bioscience Israel Ltd.	Last update: May 05, 2021

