SAP for Protocol BMS-EX-0118: Companion protocol for the ¹³C-Methacetin Breath Test (MBT) for use in Bristol-Myers Squibb phase 2b studies for BMS-986036 (PEG-FGF21), under Protocols MB130-068 and MB130-069	Document Version: 1.0
Document Nº: CSD00114	Page 17 of 21

Day 1 MBT date plus 1). Subjects will be censored at their last study visit for the following reasons:

- If a subject discontinues the study prior to the end of the study without experiencing an event
- If a subject reaches the Final Treatment visit without experiencing an event

Survival analysis will be conducted using the Cox proportional hazard model. The model summary will include the number of subjects in the model, and a table with each covariate in a separate line specifying the coefficient's value, Hazard Ratio, Hazard Ratio 95% Confidence Interval and p-value. In addition, a Kaplan-Meier plot for event-free survival will be presented, stratified by MBT parameter along with the MBT parameter log-rank p-value. Additionally, a crosstab table of MBT parameter and events will be presented.

8.4.2.2 Correlations between changes in MBT parameters and changes in other liver related parameters

Repeat MBT results (cPDR₃₀, PDR_{peak} or other breath test parameters) and their changes in subjects with and without treatment (BMS-986036) for nonalcoholic steatohepatitis (NASH) at Day 1, Week 24 and Week 48 (or Early Termination visits) will be compared and tested for correlation to baseline, as well as repeat results (change from baseline), for the following measurements:

- a. Biopsy based Fibrosis and/or NAS score
- b. Liver stiffness as measured by MRE
- c. PDFF as measured by MRI
- d. Serum Pro-C3 results
- e. Liver elastography by Fibroscan (in cohort 2 only)
- f. MELD scores (in cohort 2 only)
- g. CTP scores (in cohort 2 only)

Linear Regression will be applied in order to test for significance of the correlations between MBT and the liver measurements listed above.

Changes in MBT are measured as the difference between baseline and each of the MBT visits as well as the change in measurements between two subsequent visits in each of the two treatment groups.

Meridian Bioscience Israel Ltd.	Last update: May 05, 2021
SAP for Protocol BMS-EX-0118: Companion protocol for the ¹³C-Methacetin Breath Test (MBT) for use in Bristol-Myers Squibb phase 2b studies for BMS-986036 (PEG-FGF21), under Protocols MB130-068 and MB130-069	Document Version: 1.0
Document Nº: CSD00114	Page 18 of 21

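### SAP 8.4.1 replaces the protocol's MMRM of change in MBT with an any-increase responder rate, gives no reason for the zero cut, and leaves no baseline-adjusted dose-versus-placebo estimate of change

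*SAP*

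**What the plan says.** Protocol 9.2.1 makes an MMRM the primary analysis: "The MMRM model will include change from baseline as outcome", with arm, visit, arm-by-visit, baseline value and site as the other terms. It names fallback covariance structures in case the unstructured one fails to converge. Protocol 9.3 separately foresees a threshold: "At least one cut-off in changes of MBT values will be determined". It does not set that threshold at zero, and it does not displace the MMRM.

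SAP 8.4.1 changes the primary analysis to a responder rate for PDRpeak and cPDR30 at Weeks 24 and 48, under which "any increase of MBT value will be considered as a response while a same value or a decrease of the MBT value" is non-response. SAP section 2 states that the SAP overrides the protocol where they differ. In the SAP text supplied, MMRM survives only in the abbreviation list.

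Other relevant SAP text:
- Section 3.1.1 still asks for change from Day 1, with each dose compared individually with placebo.
- Section 4.1 says the number of subjects with valid baseline and post-treatment tests "is expected to be lower than 80, the statistical analyses" being descriptive as a result.
- Section 5.1: "There will be no imputation for missing data".
- Section 8.1: "Nominal p-values and unadjusted confidence intervals will be presented".
- Section 8.4.2.2 looks at repeat MBT results "and their changes in subjects with and without treatment (BMS-986036"), within a section on correlation with other liver measures. It names no dose contrast and no covariate.

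**The concern.** Three things are lost together.

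1. **Size of change.** A subject whose MBT rises by a trivial amount counts the same as one whose MBT doubles.
2. **A margin for noise.** If error is symmetric, a subject with no true change responds about half the time. This happens in every arm, so it dilutes the contrast rather than favouring the drug.
3. **The adjusted contrast.** SAP 8.4.1 names no between-arm comparison, effect measure or covariate, although SAP 3.1.1 requires each dose against placebo.

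The SAP explains why the study became descriptive. It does not explain why a continuous outcome was dichotomised. A small sample makes the lost information more costly.

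The primary objective is to show that MBT reflects drug response. Nominal p-values and 95% intervals will be presented and read, and SAP section 4 says the data may be used in future submissions. A null result under this analysis could come from the dichotomy or from the small sample, and readers could not tell which.

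**Working it through.** The documents state no power, effect size, SD, correlation or responder rate for MBT change, so there is no figure to reproduce. What follows shows the size of the issue under stated assumptions.

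**Inputs from the documents.** Fewer than 80 evaluable subjects (SAP 4.1); allocation 1:1:1:1 (SAP 4); two-sided nominal 5% and 95% intervals (SAP 8.1). The ceiling is 80/4 = 20 per arm.

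**Assumptions.** Effects are in SDs of change. Placebo mean change is zero (placebo response rate 50%) in the power calculations. Baseline/post-treatment correlation r is 0.6 or 0.9. Ten per arm stands for a less favourable case.

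**Step 1: information kept by the cut (small effects).** If change is normal and a proportion p respond, efficiency relative to the mean is φ(z)²/[p(1−p)], where z is the normal quantile of p.

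| p | Efficiency | Loss |
|---|---|---|
| 0.5 | 0.637 | 36% |
| 0.6 | 0.622 | 38% |
| 0.7 | 0.576 | 42% |
| 0.8 | 0.490 | 51% |

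By symmetry, the same losses apply at 0.4, 0.3 and 0.2. For heavier tails at p = 0.5, efficiency is 4f(0)²·Var: 0.757 for t with 10 df (24% loss), 0.961 for 5 df (4% loss) and 1.125 for 4 df, where the cut does better.

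**Step 2: interval width.** For a rate difference near 50%, the half-width is 1.96·√(2·0.25/n): 31 percentage points at n = 20 and 44 at n = 10. For a mean difference at n = 20 it is 1.96·√(2/20) = 0.62 SD. Near zero, a rate difference of 0.31 corresponds to 0.31/0.399 = 0.78 SD. The responder interval is therefore about 25% wider (0.78/0.62 ≈ √(1/0.637) = 1.25), before any gain from baseline adjustment.

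**Step 3: nominal power.** This comes from 10,000 simulated two-arm trials per setting. The responder column runs from Fisher to uncorrected chi-square. The adjusted column is ANCOVA of change on arm and baseline.

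| Per arm | Effect | Change distribution | Responder rate | Adjusted, r=0.6 / r=0.9 |
|---|---|---|---|---|
| 20 | 0.8 SD | normal | 0.37-0.49 | 0.77 / 0.71 |
| 20 | 0.5 SD | normal | 0.15-0.23 | 0.41 / 0.34 |
| 10 | 0.8 SD | normal | 0.12-0.24 | 0.46 / 0.39 |
| 10 | 0.5 SD | normal | 0.05-0.12 | 0.21 / 0.18 |
| 20 | 0.8 SD | t, 10 df | 0.42-0.54 | 0.78 / not run |
| 20 | 0.8 SD | t, 5 df | 0.49-0.62 | 0.79 / not run |

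In the first row an unadjusted t-test on change gives 0.69, so most of the gap is the dichotomy and a smaller part is baseline adjustment. With no effect at n = 20, rejection rates were 0.02 (Fisher), 0.04 (chi-square) and 0.05 (t-test and ANCOVA). The t rows do not contradict Step 1: Step 1 gives small-effect efficiencies against the unadjusted mean, whereas these rows use a 0.8 SD effect and include baseline adjustment.

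**Step 4: chance baseline imbalance.** A typical difference between arms of 20 is d = √(2/20) = 0.32 SD. It shifts the rate contrast by 2·[Φ((1−r)(d/2)/√(2(1−r))) − 0.5]. At r = 0.6 this is 2·[Φ(0.0707) − 0.5] ≈ 6 points; at r = 0.9 it is 2·[Φ(0.0354) − 0.5] ≈ 3 points.

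**Step 5: missing Week 48 tests.** With no imputation, a subject without a Week 48 test adds nothing to the Week 48 rate, whereas an MMRM uses the Week 24 value. If a fraction m = 0.3 is missing at random and the Week 24/48 correlation of change is ρ, the effective number is 20/[(1−ρ²)/(1−m) + ρ²]: 20/1.39 = 14.4 at ρ = 0.3 and 20/1.219 = 16.4 at ρ = 0.7, against 14.0 without the Week 24 information.

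**The case against.** The best defence is that the SAP is open about its position. It says the study is descriptive because the sample fell short, rules out formal testing, and predates the planned data release. A responder rule also answers Protocol 9.3, which wanted a cut-off in MBT change, and zero has the merit of being fixed before data access. SAP 3.1.1 still calls for change from baseline by dose, and SAP 8.1 makes mean and SD the standard summaries, so unadjusted mean change by arm may well be produced. Power is an awkward yardstick when nothing is formally tested. The size rests on assumed distributions, and with t on 4 df the cut does better. An MMRM on this sample may be fragile, and a supportive ANCOVA might be enough.

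Much of this stands as qualification. The responder rule is not foreign to the protocol, the issue is not type I error, the baseline shift (3-6 points against a half-width of 31) is small, and the missing-data gain is modest. It does not remove the point. Protocol 9.3 sat alongside the MMRM and did not replace it. General summary rules are not a specified, adjusted dose-versus-placebo contrast. A descriptive study depends on the quality of its estimates. The risk of poor fit can be handled by fallbacks.

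**Conclusion.** The concern holds. The primary analysis was changed from a baseline-adjusted model of continuous change to a rate cut at zero. No reason is given for the cut, and no adjusted dose-versus-placebo estimate on the continuous scale remains.

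This should be fixed. Confidence in the size is moderate, because the distribution, SD and correlation of MBT change are not in the documents. Under normal change the loss of information is substantial; it nearly disappears with t on 5 df and reverses with 4 df for small effects. Even the better analysis has low power at 0.5 SD or 10 per arm, so restoring it improves the estimates without making the study confirmatory.

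**What to change.** In SAP 8.4.1, specify the protocol's MMRM of change from Day 1 as the primary estimate, with arm, visit, arm-by-visit and baseline MBT, and the protocol's fallback covariance structures. State two departures from the protocol model:

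1. Use the SAP 8.5 site groups in place of individual sites.
2. In the combined analysis add cohort, which the protocol model also lacked, with site groups nested within cohort because SAP 8.5 forms them separately by cohort.

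If that model does not fit, keep cohort and drop site group. Report each dose-minus-placebo difference at Weeks 24 and 48 with a 95% interval, combined and by cohort. Keep the any-increase rate as supportive and state why zero was chosen.

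The cost is SAP wording and a little programming, with no new data. SAP section 2 leaves room for this: "any amendments to the SAP will be made prior to Exalenz independently accessing the data". Access was planned for July to November 2021, after the SAP date of May 2021; the documents do not show whether that window is still open. The downside is a model fitted to a small sample. If site groups are formed on the evaluable subjects, groups of at least 10 among at most 79 give no more than 7 groups.

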3 STUDY OBJECTIVES AND ENDPOINTS

3.1 *Study Objectives*

3.1.1 *Primary Objective*

The data generated in this companion study will be used to demonstrate the ability of the MBT to evaluate patient response to treatment with BMS-986036, comparing placebo to each treatment arm individually. Primary efficacy assessment will be performed using the Week 24 and the Week 48 visit measures compared to Day 1 (change from baseline) for the combined population of the two cohorts, according to availability, by dose of the BMS drug under study.

The same assessments for each study cohort independently will be reported.

3.1.2 *Secondary Objective*

The following assessments will be done by treatment arm by dose of the BMS drug under clinical investigation and combined arms on the combined population of the two study cohorts:

1. To demonstrate the short and long-term prognostic value (3 months, 6 months and 1 year, respectively) of MBT for liver disease deterioration (reported as liver-related

Meridian Bioscience Israel Ltd.	Last update: May 05, 2021
SAP for Protocol BMS-EX-0118: Companion protocol for the ¹³C-Methacetin Breath Test (MBT) for use in Bristol-Myers Squibb phase 2b studies for BMS-986036 (PEG-FGF21), under Protocols MB130-068 and MB130-069	Document Version: 1.0
Document Nº: CSD00114	Page 9 of 21

clinical outcome events). Assessment will be performed using MBT from the Day 1, Week 24 and Week 48 visits.

2. To assess the ability of changes in the MBT to reflect biopsy proven changes in fibrosis and/or NAS as assessed by a central reader, where available, at Week 24 (or at least Week 20 in cases of an Early Termination time point) (for cohort 1) or at Week 48 (for cohort 2) compared to the baseline biopsy from the screening visit.
3. To assess the ability of changes in the MBT to reflect changes in liver stiffness as measured by Magnetic Resonance Elastography (MRE), where available, at Week 24 and Week 48 (or at Early Termination) compared to baseline MRE from the screening visit.
4. To assess the ability of changes in the MBT to reflect changes in Proton Density Fat Fraction (PDFF) as measured by Magnetic Resonance Imaging (MRI), where available, at Week 24 and Week 48 (or Early Termination), compared to baseline MRI from the screening visit.

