4 STUDY DESIGN

Please refer to BMS' protocols MB130-068 and MB130-069 - IND 125297.

This study is a feasibility companion protocol that will rely on the data generated by BMS's studies of BMS-986036 (PEG-FGF21) under protocols MB130-068 and MB130-069 (IND 125297), which are defined in this companion protocol as two separate study cohorts (1 and 2, respectively) with the exception of the MBT, for which Exalenz may extract additional data based on the recorded MBT results. The MB130-068 and MB130-069 studies are Phase 2b, multicenter, double-blind, randomized, placebo-controlled, parallel-group studies to demonstrate the safety and efficacy of BMS-986036 in the treatment of subjects with NASH and stage 3 liver fibrosis or compensated cirrhosis with up to 48 weeks of treatment. The study is feasibility for drug response monitoring however the data may be used by Exalenz for future submissions.

As described in the BMS protocols, subjects will be enrolled and randomized via interactive response technology (IRT) to receive BMS-9860936 10mg QW, BMS-986036 20mg QW, BMS-9860936 40mg QW or matching placebo QW in a 1:1:1:1 ratio.

The BMS studies' treatment durations will each consist of two periods:

1. A 48-week, Double-Blind Treatment Period, during which the subjects will receive blinded study medication (BMS-986036 10mg, 20 mg, 40mg QW or matching placebo QW). During the Double-Blind Treatment Period, subjects will be evaluated for safety and efficacy every 4 weeks (± 5 days) through Week 24 and every 8 weeks (± 5 days) from Week 24 through Week 48.
2. A Follow up period, during which subjects will be evaluated for safety and efficacy for 4 weeks through Week 52.

Meridian Bioscience Israel Ltd.	Last update: May 05, 2021
SAP for Protocol BMS-EX-0118: Companion protocol for the ¹³C-Methacetin Breath Test (MBT) for use in Bristol-Myers Squibb phase 2b studies for BMS-986036 (PEG-FGF21), under Protocols MB130-068 and MB130-069	Document Version: 1.0
Document Nº: CSD00114	Page 12 of 21

3. A Follow up period of at least 6 months and up to 14 months after the Week 52/ PTFU Visit for the collection of additional DXA assessment (in all participants) and immunogenicity assessments (in participants for whom Long-Term Immunogenicity Follow-Up Visits are required.) Any liver related complication event will be recorded.

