The last dose of study medication will be at the Week 48 visit. Subjects will have a safety and efficacy evaluation at week 48 and return for a post-treatment follow-up evaluation through Week 52.

As a sub-study of BMS protocols MB130-068 and MB130-069, MBT will be performed at the Day 1 visit and every 24 weeks during the Double-Blind Treatment Period in order to allow the assessment whether BMS-986036 compared to placebo improves liver metabolic function as determined by the MBT.

4.1 *Sample Size Considerations*

Subjects, that were enrolled into two separate BMS sponsored IND studies (MB130-068, MB130-069, respectively) at selected study sites, were offered the opportunity to perform the MBT, and are considered as two separate study cohorts (cohort 1 and 2, respectively) for this companion protocol. Each cohort consists of four treatment arms (BMS-986036 10mg, 20mg, 40mg QW or matching placebo QW) as defined in the respective BMS sponsored protocols.

Cohort 1 consists of subjects with NASH and stage 3 fibrosis, as assessed by a central laboratory reader of the liver biopsies, and who meet all the MB130-068 study criteria. The sample size for this MB130-068 study is n=160.

Cohort 2 consists of subjects with NASH and compensated liver cirrhosis (stage 4 fibrosis) as assessed by a central laboratory reader of the liver biopsies, and who meet all the MB130-069 study criteria. The sample size for this MB130-069 study is n=100.

This feasibility companion protocol includes those two cohorts of subjects, which were planned for up to 260 subjects) from approximately 75 sites worldwide (USA and Japan) for the two BMS IND studies, while the MBT was only conducted in the USA.

It was expected that not all participating sites would elect to perform the MBT. The total number of subjects expected to perform the MBT was initially planned for up to 250 subjects (also accounting for drop outs). Each subject would perform up to 3 MBTs over 1 year.

Meridian Bioscience Israel Ltd.	Last update: May 05, 2021
SAP for Protocol BMS-EX-0118: Companion protocol for the ¹³C-Methacetin Breath Test (MBT) for use in Bristol-Myers Squibb phase 2b studies for BMS-986036 (PEG-FGF21), under Protocols MB130-068 and MB130-069	Document Version: 1.0
Document Nº: CSD00114	Page 13 of 21

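### The pooled primary responder comparison is not stratified by cohort, so chance differences in cohort mix can move the dose-versus-placebo differences; the effect is small and free to remove

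*SAP*

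**What the plan says.** SAP 3.1.1 makes the primary assessment the change from Day 1 at Week 24 and Week 48, comparing placebo with each dose "for the combined population of the two cohorts, according to availability, by dose of the BMS drug under study". SAP 8.4.1 turns this into a responder analysis in which "any increase of MBT value will be considered as a response" and an unchanged or lower value is a non-response. The analysis is run on the mEA set using the "responder rate of Week 24 and Week 48 of data from both BMS' studies". Neither section names a comparison method, a stratification factor or a cohort covariate for the pooled comparison.

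Cohort enters the primary analysis only through separate reporting (SAP 3.1.1, 8.4.1 and 8.5). SAP 8.5 builds site groups within cohort. These serve separate site reports and an interaction term in the linear and Cox models, not the pooled responder comparison.

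On design, SAP 4 says subjects are randomised to three doses "or matching placebo QW in a 1:1:1:1 ratio". SAP 4.1 says of cohort 1 (stage 3 fibrosis) "The sample size for this MB130-068 study is n=160" and of cohort 2 (compensated cirrhosis) "The sample size for this MB130-069 study is n=100". The number with valid baseline and post-treatment breath tests, "across both BMS studies, is expected to be lower than 80". All analyses are descriptive with nominal p-values (SAP 6.1), and unadjusted 95% intervals are to be shown (SAP 8.1).

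**The concern.** Each subject was randomised inside one of two trials, so cohort is a randomisation stratum by construction as well as a marker of disease stage. Combining the trials into one responder proportion per arm ignores that stratum. If two arms happen to hold different proportions of stage 3 and cirrhotic subjects, and those groups differ in their chance of any MBT increase, part of the pooled difference reflects cohort mix rather than dose.

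Two features make this worth a sentence in the SAP. All three dose comparisons share one placebo arm, so an unlucky placebo mix moves all three in the same direction at that visit. And because the study is descriptive, its message rests on point estimates and intervals, of which the SAP makes the pooled one primary.

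**Working it through.** **Plan's own figure.** The documents give no responder rate, variance, effect size or power for the primary endpoint, so there is nothing to reproduce beyond 160 + 100 = 260, which agrees with the stated total.

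**Inputs from the documents.** Allocation 1:1:1:1 in both trials (SAP 4). Parent sizes 160 and 100, so cohort 1 share = 160/260 = 0.615 (SAP 4.1). Analysable number below 80, so at most 79, or 79/4 ≈ 20 per arm.

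**Assumptions not in the documents.** The breath-test subset has the parent mix (a 50% share was also tried). Allocation is simple, without blocking. Responder probabilities are 0.5 v 0.4, 0.5 v 0.3, 0.6 v 0.3 and 0.7 v 0.3 in cohorts 1 and 2, giving gaps of 10, 20, 30 and 40 points. There is no drug effect.

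**Formula.** Shift in the crude pooled difference = (difference between the two arms in cohort 1 share) × (difference between cohorts in responder probability).

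**By hand.** With 19 per arm, the SD of the difference in share is √(2 × 0.615 × 0.385 / 19) = 0.158, or about 16 points. A 20-point gap gives 0.158 × 0.2 = 0.032; a 40-point gap gives 0.158 × 0.4 = 0.063. With no gap the shift is zero.

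**Example.** Suppose 15 of 20 dose subjects and 10 of 20 placebo subjects come from cohort 1, with responder probabilities 0.5 and 0.3. Expected rates are 0.75 × 0.5 + 0.25 × 0.3 = 0.45 and 0.50 × 0.5 + 0.50 × 0.3 = 0.40. The crude difference is 5 points with no drug effect; within each cohort it is zero.

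**Simulation.** 200,000 runs per scenario, N = 79, 62% in cohort 1. The last four columns are nominal two-sided rejection rates.

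| Cohort gap | SD of shift | 95th percentile of absolute shift | SD of crude difference | SD stratified | Crude test, overall | Crude test, shares differ ≥20 points | Stratified test, overall | Stratified test, shares differ ≥20 points |
|---|---|---|---|---|---|---|---|---|
| 10 | 1.6 | 3.1 | 16.2 | 16.3 | 5.2% | 5.3% | 4.9% | 4.8% |
| 20 | 3.2 | 6.2 | 16.1 | 16.0 | 5.3% | 6.5% | 5.0% | 5.0% |
| 30 | 4.8 | 9.3 | 16.2 | 15.7 | 5.2% | 7.3% | 4.9% | 4.8% |
| 40 | 6.4 | 12.4 | 16.2 | 15.1 | 5.2% | 9.3% | 4.9% | 4.9% |

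The shift averages zero in every row. Its share of the variance of the crude difference is about 1%, 4%, 9% and 15%; for the 20-point gap, (3.17/16.09)² = 0.039.

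Cohort shares differ by 20 points or more in about 21% of realisations at N = 79, 27% at N = 60 and 36% at N = 40. At N = 40 the SD of the shift runs from 2.2 to 8.7 points, but the crude SD is then about 23 points. A 50% share at N = 79 gives 1.6 to 6.5 points. At the planned 250 subjects, a 20-point gap would give 1.8 points.

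**The case against.** The other side has a good deal to say, and most of it stands as a limit on weight.

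- **No bias.** A reader might infer that dose is confounded with cohort. It is not: the allocation ratio is the same in both trials, so cohort is unrelated to dose by design and the imbalance averages zero. The crude test's overall error rate is close to nominal because chance variation in cohort mix is part of its ordinary sampling variation.
- **Level is not change.** A reader might infer from protocol 3.2, which says advanced disease gives low MBT values, that cirrhotic subjects have a different chance of responding. That passage concerns level. The endpoint is the sign of a within-subject change, and no passage links disease stage to that.
- **Imbalance is possible, not certain.** The mix of the US-only, opt-in subset is not given, and any blocking in the parent trials is set out in protocols not available here.
- **The protocol's mixed model.** A reader might extend the point to that model, since "The MMRM model will include change from baseline as outcome, and Study Arm, Visit, Study Arm*Visit Interaction, Baseline value and site as covariates" lists no cohort term. This is moot: the SAP replaces the model with the responder analysis and states that it prevails where the two differ (SAP 2).
- **Already visible.** Cohort-specific results and disposition by cohort and treatment group are planned (SAP 8.3, 8.4.1, 8.5), so a reader could calculate a stratified difference from the counts.
- **Unspecified, not excluded.** No comparison method is named, so stratification is not ruled out, and the analyses are descriptive.

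What survives is narrow. The estimate called primary is the pooled one. Separate tables reveal an imbalance but do not remove it from that estimate, and the stratified version is not pre-specified.

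**Conclusion.** The point holds as a minor one. The primary comparison pools two separately randomised trials without using the cohort stratum. No systematic bias follows from the allocation. For a cohort gap of 10 to 40 points, cohort mix adds a mean-zero shift with an SD of about 1.6 to 6.4 points, well below the sampling SD of about 16 points. Error rates move noticeably only in the minority of realisations with a large imbalance, and then only for the wider gaps.

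These sizes rest on 79 subjects, the parent-trial mix, simple allocation and an assumed gap that the documents neither give nor imply. If the cohorts respond alike, the shift is zero. The statement about bias concerns allocation; it does not cover loss of valid follow-up tests that differs by arm and cohort. The documents give no evidence of such loss, and a cohort-by-arm table at each visit would show it.

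The case for acting is that analysing by the groups already randomised removes the shift at almost no cost, not that the crude result would be misleading.

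**What to change.** Before the sponsor accesses the data, add to SAP 8.4.1 that each pooled dose-versus-placebo responder difference, for PDRpeak and cPDR30 at Week 24 and at Week 48, is a Mantel-Haenszel risk difference stratified by cohort with a 95% CI, and that any nominal p-value comes from the Cochran-Mantel-Haenszel test with the same strata. Tabulate cohort by arm for the mEA set at each visit. Keep the separate cohort tables.

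A model-based adjustment is less suitable here: with about 19 per arm, 19 × 0.615 ≈ 12 and 19 × 0.385 ≈ 7 subjects per arm fall in the two cohorts, so a logistic fit risks separation.

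The cost is SAP wording. No new data are needed, and SAP 2 allows amendment until data access. Precision is essentially unchanged: the SD rises from 16.2 to 16.3 points at a 10-point gap, and falls from 16.1 to 16.0 at 20 points and from 16.2 to 15.1 at 40 points. The same sentence also supplies the comparison method that SAP 8.4.1 does not yet name.
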